9.3 Sample Size and Accrual

9.3.1 The primary comparison is of baseline RHI between the HIV/HCV coinfecting and HIV monoinfected groups. The estimated difference in RHI between the 2 groups is assumed to be the difference between high-risk CVD (HIV/HCV) and moderate-risk CVD (HIV). RHI is expected then to be 1.6 in HIV/HCV and 1.3 in HIV, with standard deviation (SD) of 0.37.⁵² With a sample size of 80 HIV/HCV and 40 HIV, we have an estimated power of 99% for detection of the expected difference in RHI between the HIV/HCV and HIV groups. However, if we conservatively estimate the difference in baseline RHI to be 0.2 between the 2 groups, we will have 80% power with this sample size. For select secondary analyses of differences in the CVD biomarkers of sICAM-1 (expected difference of 779 vs 1284 ng/mL, SD=526) and sE-selectin (118 vs 223 ng/mL, SD=190),³⁰ we will have 99% and 81% power, respectively, with this sample size.

Accrual of about 20 subjects per month is expected, to complete enrollment in 6 months.

9.3.2 With 80 HCV/HIV subjects, we will have 80% power to detect a correlation between any one marker and RHI of > 0.31 . With 40 HIV subjects, we will have 80% power to detect a correlation > 0.42 , correlations that have been seen in other populations.^{53,54}

9.3.3 Among 80 HIV/HCV subjects, we expect about 40 (50%) will initiate HCV treatment. Out of 40 who initiate HCV treatment, we expect about 27 (67%) will be responders and 13 will be non-responders. To compare responders (n=27) with subjects without treatment (n=40), we will have 80% power to detect a difference of 0.7 in effect size. To compare HIV monoinfected controls (n=40)

and untreated HIV/HCV subjects, we will have 80% power to detect a difference of 0.63 in effect size.

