9.4 Data Analysis Plan

9.4.1 Objective: To determine the effect of HCV coinfection on endothelial function in the HIV-1-infected cohort at baseline.

Descriptive statistics, including mean, SD, median, minimum, maximum, and interquartile range, will be provided for the overall cohort, by HCV status, and by PAT performance site for baseline patient characteristics, RHI, CVD biomarkers, HOMA-IR, hemoglobin A1c, and FRS. Histograms and scatter plots will be produced to visually inspect the distributions and pairwise association. Log-transformation as necessary will be done for RHI, if its distribution is found to be skewed. ANOVA (analysis of variance) will be used to compare continuous variables by HCV status and site and Chi-square test will be used to compare categorical variables. All tests will be 2-sided and a p-value less than 0.05 will be considered statistically significant.

Two sample t-test or Wilcoxon rank sum will be performed to compare RHI in the HIV/HCV vs HIV groups. Multiple linear regression analysis will also be carried out to compare RHI in HIV/HCV vs HIV, adjusting for PAT performance site and any differences in baseline characteristics including CD4 nadir and ART type. Subgroup analyses by race/ethnicity and gender will be conducted. Similar analyses will be carried out to compare biomarkers between the HIV/HCV and HIV groups. Given multiple comparisons, in addition to unadjusted p-values, we will report significance according to Benjamini-Hochberg false discovery rate method.⁵⁵

9.4.2 Objective: To assess whether non-hepatic biomarkers of endothelial dysfunction, inflammation, and thrombosis (sICAM-1, sE-selectin, Lp-PLA2, IL-6, and D-dimer) are better correlates of endothelial function than traditional hepatic-derived biomarkers (hsCRP and lipids) in HIV/HCV-coinfected in cross-sectional assessment.

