Correlation analysis (Pearson or Spearman) will be conducted to evaluate the association of each circulating biomarker as the predictor and RHI as a continuous outcome variable. Further correlation of biomarkers with each other and with RHI will be performed by use of correlation matrices. Multiple linear regression models will be used while controlling for confounders as in Aim 1 analysis, but with each biomarker as the primary independent variable to determine the contribution of each biomarker as a predictor of RHI. A final model will be constructed by including all significant biomarkers to predict RHI. The adjusted R-squared value will be used to indicate the predictive ability of the model. Similar analysis will be carried out in HIV-monoinfected subjects only to derive the RHI prediction model. The models for each cohort will be compared to each other for their predictive ability and differences in individual biomarker

significance in each cohort. This analysis will allow us to define whether non-hepatically-derived biomarkers have stronger correlation with RHI than hepatically-derived biomarkers.

9.4.3 Objective: To determine the effect of HCV co-infection and HCV virologic suppression post treatment on endothelial function and CVD biomarkers in the HIV-1-infected cohort over one year of follow-up.

Change in RHI and change in biomarkers from baseline to follow-up will be compared among 4 groups of subjects (HCV treatment responders and non-responders, untreated HIV/HCV subjects, and HIV controls). Boxplots will be used to visually display the difference among 4 groups. Pair-wise comparison will be carried out based on 2-sample t-test or Wilcoxon test. ANCOVA will be carried out to compare among 4 groups adjusting for baseline values and demographic characteristics and other baseline confounders. Adjusted comparison between any 2 groups will be estimated based on appropriate contrast. Correlation analysis will be carried out between change in biomarkers and change in RHI.

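### Section 9.4.2 takes predictive ability from the adjusted R-squared of a model whose markers were selected on the same subjects; this overstates performance in new subjects, about twice as much at n=40 as at n=80

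*Combined protocol and SAP*

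**What the plan says.** Section 9.4.2 starts with correlations between each biomarker and RHI. It then fits confounder-adjusted regressions "with each biomarker as the primary independent variable to determine the contribution of each biomarker as a predictor of RHI". The selection step follows: "A final model will be constructed by including all significant biomarkers to predict RHI". The performance measure is given in one sentence: "The adjusted R-squared value will be used to indicate the predictive ability of the model".

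The procedure is then run again in the other cohort: "Similar analysis will be carried out in HIV-monoinfected subjects only to derive the RHI prediction model". The results are set against each other: "The models for each cohort will be compared to each other for their predictive ability and differences in individual biomarker" significance.

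The only significance threshold is in section 9.4.1: "All tests will be 2-sided and a p-value less than 0.05 will be considered statistically significant". Section 9.3.2 gives the cohort sizes, 80 and 40. The documents contain no bootstrap, cross-validation, hold-out sample, shrinkage or confidence interval for R-squared.

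**The concern.** Adjusted R-squared charges for the terms that end up in the model. It does not charge for the candidates that were tried and discarded. When markers enter because they were significant in these subjects, their fitted contribution is biased upward, and the adjustment does not see it.

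The bias is larger in the smaller cohort, because a marker needs a larger sample correlation to reach p<0.05 there. The plan then compares this figure between 80 and 40 subjects, so the comparison is tilted towards the HIV-monoinfected model.

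At stake are the plan's statements on how well markers predict RHI and on which cohort is better predicted. Section 2.1 (Rationale) says the project is meant to supply preliminary data for further funding, so an inflated R-squared would carry into the planning of the next study.

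**Working it through.** **Inputs from the documents.** n=80 and n=40 (9.3.2); two-sided 0.05 (9.4.1); five non-hepatic markers plus hsCRP and lipids (9.4.2). 

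**Assumptions.** The number of lipid components is not fixed for this analysis; 1 to 4 gives 7 to 10 candidates. The correlation between markers (0 or 0.3), the number of confounders (0 to 4) and the true R-squared are also assumed.

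**1. The plan's own figures.** The plan states "With 80 HCV/HIV subjects, we will have 80% power to detect a correlation between any one marker and RHI of > 0.31", and "With 40 HIV subjects, we will have 80% power to detect a correlation > 0.42". By Fisher z, power = Φ(atanh(r)·√(n−3) − 1.96).
- n=80, r=0.31: 0.3205 × 8.775 − 1.96 = 0.853, power 80.3%.
- n=40, r=0.42: 0.4477 × 6.083 − 1.96 = 0.763, power 77.7% (78.6% by simulated t-test).

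Both reproduce to within about two points. They are powers for single markers and say nothing about model performance.

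**2. The floor set by selection.** For one marker and no confounders, significance needs |r| ≥ t/√(t² + n − 2), and adjusted R² = 1 − (1 − r²)(n − 1)/(n − 2).
- n=80: t=1.991, |r| ≥ 0.220, adjusted R² ≥ 1 − 0.9516 × 79/78 = 0.036.
- n=40: t=2.024, |r| ≥ 0.312, adjusted R² ≥ 1 − 0.9027 × 39/38 = 0.074.

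A selected one-marker model cannot report less than this, whatever the truth. The floor is about twice as high at n=40.

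**3. Chance of a model under no association.** With independent markers it is 1 − 0.95^7 = 30% to 1 − 0.95^10 = 40%. With 10 markers correlated 0.3, simulation gives 35 to 38%.

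**4. Size of the overstatement.** Simulation with 10 markers, inter-marker correlation 0.3 and no confounders: screen each marker at p<0.05, refit the survivors, then compare adjusted R² with the R² of the same fitted coefficients in new subjects.

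| Truth, same in both cohorts | Averaged over | Adjusted R², n=80 / n=40 | Out-of-sample R², n=80 / n=40 | Gap, n=80 / n=40 |
|---|---|---|---|---|
| No association | studies that select a marker | 0.07 / 0.13 | -0.10 / -0.19 | 0.17 / 0.32 |
| One real marker, r=0.31 | all studies | 0.11 / 0.12 | 0.03 / -0.04 | 0.08 / 0.16 |
| All markers at r=0.31 | studies that select a marker (nearly all) | 0.26 / 0.30 | 0.17 / 0.10 | 0.09 / 0.20 |

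In the last row the 40-subject model looks better and predicts worse.

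**5. Range over other assumptions, averaged over all studies.** With 7 to 10 markers and no true association, the gap is 0.05–0.08 (n=80) and 0.10–0.15 (n=40) without confounders, and 0.11–0.14 and 0.24–0.29 with four null confounders. With true R² of 0.05 to 0.30 and no confounders it is 0.04–0.11 and 0.09–0.20.

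**6. Ranking of the cohorts.** With true R² of 0.10 (n=80) and 0.05 (n=40), the 40-subject model shows the higher adjusted R² although its out-of-sample R² is lower in 32–44% of studies. With 0.15 and 0.05 it does so in 24–34%.

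**The case against.** **Sampling error.** A reader might infer that screening causes most of the disagreement between the cohorts. The calculations do not support that. A prespecified 10-marker model with no screening has nearly unbiased adjusted R-squared (0.254 and 0.245 against a true 0.26). Yet its two values differ by more than 0.10 in 55–58% of studies when markers are real, against 42–51% with screening. At true R-squared of 0.10 and 0.05 it also ranks the 40-subject cohort higher in about 35–40% of studies. This objection stands: the instability is largely the size of the smaller cohort. The upward bias is separate and correctable.

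**A reversal is not the expected result.** Averaged over all studies at true R-squared 0.10 and 0.05, including those that select nothing, mean adjusted R-squared keeps the right order. The means reverse only among studies where both cohorts yield a model (0.12–0.13 against 0.15–0.17). The ranking can reverse; nothing shows that it will.

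**What is being estimated.** With all markers at r=0.31 the population R-squared is 10 × 0.31²/(1 + 9 × 0.3) = 0.961/3.7 = 0.26, so 0.26 at n=80 is on target as a measure of association. That stands, but the plan uses the figure for predictive ability, which is the other quantity. Out-of-sample R-squared also falls with n even when the biology is identical, so correcting for optimism does not by itself make the comparison fair.

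**False discovery rate.** Section 9.4.1 reports Benjamini-Hochberg results beside unadjusted p-values; 9.4.2 does not say they govern selection. If they did, the average gap under no association and no confounders would shrink to about 0.024 and 0.045–0.053, still about double at n=40.

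**Confounders.** A reader might infer that the final R-squared necessarily includes what the confounders explain. The text places them in the single-marker models and is not explicit about the final one.

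**Reach.** Primary objective 1.2.3 concerns marker type within HIV/HCV and is also served by the correlations and single-marker regressions. The defect touches the predictive-ability statements, not the whole objective.

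**Conclusion.** The concern holds for the measure of predictive ability. After selection at p<0.05 on the same subjects, adjusted R-squared overstates performance in new subjects in both cohorts, and by about twice as much at n=40. In the table above the overstatement runs from 0.08 to 0.17 at n=80 and from 0.16 to 0.32 at n=40. The exact values rest on the assumed marker count, correlations and true effects. The direction and the rough doubling held in every setting tried.

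The comparison of the two cohort models is therefore tilted towards the smaller cohort and can point the wrong way. The documents do not support the stronger claims that it will reverse, or that selection explains most of the spread between cohorts.

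**What to change.** Keep the model-building steps of 9.4.2. In each bootstrap resample, repeat the whole procedure (screening plus refit). Report the optimism-corrected R-squared with a confidence interval per cohort, and use it in place of adjusted R-squared wherever predictive ability is stated. State whether the final model carries the Aim 1 confounders; if it does, report the increment over the confounder-only model.

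For the cohort comparison, give the confidence interval of the difference, note that out-of-sample R-squared depends on n, and describe the comparison as exploratory. A difference in point estimates between the 80- and 40-subject models should not be read as a difference between cohorts.

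Expected gain: with all markers at r=0.31 the bootstrap gives 0.20 (n=80) and 0.16 (n=40) against true values of 0.17 and 0.10, so the overstatement falls from 0.09 to 0.03 and from 0.20 to 0.06. With one real marker, over all studies, it gives 0.015 and -0.054 against 0.029 and -0.042. The ranking is helped but not cured. Cross-validation with screening inside each fold lowered the share of studies ranking the 40-subject model higher from 38% to 24% (true R-squared 0.10 and 0.05), and from 29% to 19% (0.15 and 0.05).

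The cost is a few lines of code and of plan text, with no new data. The reported R-squared will be lower, and the cohort comparison will remain imprecise.

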hsCRP	high-sensitivity C-reactive protein
IATA	International Air Transport Association
ICF	informed consent form
ICH	International Conference on Harmonisation
IFN	interferon
IL-6	interleukin-6
INR	international normalized ratio
IRB	institutional review board
LAB	LA Biomed/Harbor-UCLA
LDL	low-density lipoprotein cholesterol
LPC	Laboratory Processing Chart
Lp-PLA2	lipoprotein-associated phospholipase A2
NIH	National Institutes of Health
OHRP	Office for Human Research Protections
OI	opportunistic infection
PAT	peripheral arterial tonometry
PEG-IFN	pegylated interferon

RBV	ribavirin
RHI	reactive hyperemia index
RNA	ribonucleic acid
SAE	serious adverse event
sICAM-1	soluble ICAM-1
sP-selectin	soluble P-selectin
SVR	sustained virologic response
TC	total cholesterol
TG	triglycerides
WBC	white blood cell
UCLA-WW	UCLA-Westwood

SCHEMA

Clinical and Translational Science Institute Prospective Longitudinal Assessment of Coinfected Subjects with HIV/Hepatitis C for Endothelial Function Study (CTSI-PLACE Study)

DESIGN	Prospective, observational, longitudinal cohort of HIV/HCV coinfecting subjects matched to HIV monoinfected controls with primary cross-sectional analysis of baseline endothelial function and circulating cardiovascular biomarkers.
DURATION	Subjects will be on study for a minimum of 52 weeks. Those who initiate HCV treatment will be on study for at least 24 weeks after end of HCV treatment.
SAMPLE SIZE	A total of 120 subjects will be enrolled in the study (80 HIV/HCV coinfecting and 40 HIV monoinfected subjects).
POPULATION	Group A: 80 HIV/HCV coinfecting subjects Group B: 40 HIV monoinfected subjects All subjects ≥ 18 years of age without known CVD at baseline with CD4 cell count ≥ 200 cells/mm ³ and HIV-1 RNA < 50 copies/mL within 120 days of study entry and on stable antiretroviral therapy (ART) since the time of last CD4 and HIV-1 RNA measurement. Those with a HCV infection must have HCV RNA $\geq 10,000$ IU/mL. The two groups will be frequency matched based upon age, race, sex, diabetes, smoking status, hormonal therapy and statin use, and CD4 cell count at baseline.

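### Section 9.4.2 compares the HIV/HCV and HIV marker models partly by which biomarkers are significant in each cohort; this is not a test of a difference, and the 80/40 split tilts it toward HIV/HCV-only findings

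*Combined protocol and SAP*

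**What the plan says.** Section 9.4.2 correlates each biomarker with RHI, fits adjusted regressions with one biomarker at a time, and then selects: "A final model will be constructed by including all significant biomarkers to predict RHI". Adjusted R-squared describes how well the model predicts. The exercise is repeated in the smaller cohort: "Similar analysis will be carried out in HIV-monoinfected subjects only to derive the RHI prediction model". The two resulting models are then "compared to each other for their predictive ability and differences in individual biomarker" significance within each cohort. There are thus two criteria, adjusted R-squared and the pattern of significant markers.

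The Schema sets the cohorts at 80 and 40. Section 9.4.1 fixes the significance rule: "All tests will be 2-sided and a p-value less than 0.05 will be considered statistically significant". Section 9.3.2 acknowledges that the cohorts differ in sensitivity: "With 80 HCV/HIV subjects, we will have 80% power to detect a correlation between any one marker and RHI of > 0.31", and "With 40 HIV subjects, we will have 80% power to detect a correlation > 0.42".

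Section 9.4 contains no marker-by-HCV interaction, no test of a difference between two correlations, and no pooled model with a separate marker slope for each cohort. The contrasts in 9.4.3 concern change over follow-up in four groups, which is a different question.

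**The concern.** Two p-values on opposite sides of 0.05 can come from estimates that hardly differ. A rule that reads discordant significance as a difference between cohorts will therefore report differences where there are none.

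With cohorts of 80 and 40 the errors are also lopsided, because the larger cohort reaches significance with a weaker observed correlation. At stake is any statement that a marker tracks endothelial function in coinfected subjects but not in monoinfected ones. Under the written rule such a statement could reflect cohort size and chance rather than HCV.

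**Working it through.** **Inputs.** Cohorts of 80 and 40 (Schema); two-sided 0.05 (9.4.1); stated detectable correlations of 0.31 and 0.42 at 80% power (9.3.2). The true correlations are not known, so a range is used. The number of covariates is not stated; none is assumed first, then eight as an illustration.

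**The plan's own figures.** Detectable r = tanh[(1.960 + 0.842)/√(n − 3)].
- n = 80: tanh(2.802/8.775) = 0.309. This reproduces 0.31.
- n = 40: tanh(2.802/6.083) = 0.431. Power at 0.42 is 77.7% by this formula and 78.7% by simulation. The stated 0.42 is slightly generous, but not enough to matter.

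**Observed correlation needed for p < 0.05.** r = t/√(n − 2 + t²), giving 0.220 at n = 80 and 0.312 at n = 40.

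**Same true r in both cohorts.** Power = Φ[atanh(r)·√(n − 3) − 1.96], plus a negligible lower tail except near r = 0. At r = 0.31, atanh(r) = 0.3205:
- n = 80: Φ(2.813 − 1.96) = 0.803
- n = 40: Φ(1.950 − 1.96) = 0.496

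The cohorts are independent, so:
- significant in HIV/HCV only: 0.803 × (1 − 0.496) = 0.405
- significant in HIV only: 0.496 × (1 − 0.803) = 0.098

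| True r, both cohorts | Power n = 80 | Power n = 40 | HIV/HCV only | HIV only |
|---|---|---|---|---|
| 0 | 5% | 5% | 4.8% | 4.8% |
| 0.20 | 43% | 23% | 33% | 13% |
| 0.31 | 80% | 50% | 40% | 10% |
| 0.42 | 97% | 78% | 22% | 2% |
| 0.50 | 99.8% | 92% | 8% | 0.2% |

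Without covariates, the HIV/HCV-only probability peaks at about 42%, near r = 0.28. With eight assumed covariates (r read as a partial correlation) it is 45% at r = 0.31 and 31% at r = 0.42.

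**How much is due to the 2:1 split.** With 60 per cohort and r = 0.31, the discordance is 22% in each direction, 44% in all. At 80/40 it is 40% and 10%, 50% in all. Separate testing creates most of the discordance; the unequal sizes mainly give it a direction.

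**A direct test under the same conditions.** The standard error of the Fisher-z difference is √(1/77 + 1/37) = 0.200. This test declares a difference in 5% of cases when the relations are identical. Among results that are significant in HIV/HCV only at a common r of 0.31, it is significant in only about 6%.

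**The case against.** The strongest reply is that the between-cohort comparison is not what the study is for. Hypothesis 1.1.2, objective 1.2.3 and the closing sentence of 9.4.2 all ask whether non-hepatic markers do better than hepatic ones, and the hypothesis and objective ask it within HIV/HCV subjects. That is right. A reader might infer that cohort size alone could deliver hypothesis 1.1.2, but the documents do not support this. Going from 40 to 80 subjects raises power for hepatic and non-hepatic markers alike, and the plan nowhere says that a discordant marker will be called specific to HCV.

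A reader might also infer that identical relations will routinely look different because of the 80/40 split. For a given marker that is too strong: the chance stays below one half, and is under 10% at r = 0 and at r = 0.50. Nor does the near-certainty of some discordance across many markers show an effect of the split. With ten markers (an assumed number), all at r = 0.31 and correlated 0.3 with each other, at least one is discordant in about 99% of simulated studies at 80/40, but also in 98.5% at 60/60.

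Two further defences fail. Adjusted R-squared is named before significance, but each model holds only markers chosen by significance in its own cohort, and no interval or test for the difference in adjusted R-squared is planned. The Benjamini-Hochberg reporting in 9.4.1 is not stated to cover 9.4.2, and a stricter threshold does not remove the tilt: at a two-sided 0.01, the HIV/HCV-only probability at r = 0.31 is 0.594 × (1 − 0.266) = 44%.

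**Conclusion.** The point holds for the planned between-cohort comparison and no further. One of the two stated criteria is not a valid test of a difference. With equal true correlations of about 0.2 to 0.4, a marker has roughly a 22% to 40% chance of being significant in HIV/HCV only, against 2% to 13% for HIV only. At r = 0 the two directions are equal, at about 5%. If all five non-hepatic markers had r = 0.31 in both cohorts, about two (5 × 0.405) would be expected to appear in HIV/HCV only.

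These figures assume full enrolment at 80 and 40, approximately normal data, the 0.05 threshold and, in the main table, no covariates. The baseline RHI comparison, which is the primary one, and the within-HIV/HCV marker question are unaffected. This should be fixed, but it does not threaten the main result.

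**What to change.** In 9.4.2, replace the comparison of significance by cohort with one pooled model per marker in all 120 subjects: RHI on marker, HCV status, marker-by-HCV status and the planned covariates. Report the difference in slopes with its 95% confidence interval, and base any claim that a marker behaves differently by HCV status on that term alone. The cohort-specific models can stay as description. State whether the false discovery rate reporting covers the interaction terms.

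The change costs some wording and one model per marker, with no new data or subjects. The drawback is that the limited ability to separate the cohorts becomes visible. As an approximation on the correlation scale, which matches a slope difference only if marker and residual variances are equal across cohorts, 80% power needs a Fisher-z gap of 2.802 × 0.200 = 0.56, for example r = 0.51 against 0. The plan should say so and treat the interval as the main result, since a non-significant interaction will not show that the cohorts are alike.

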1.2 Primary Objectives

- 1.2.1 To establish a UCLA CTSI-wide cohort of demographically diverse HIV/HCV coinfecting and matched HIV mono-infected men and women with HIV suppressed on stable antiretroviral therapy (ART).
- 1.2.2. To determine the effect of HCV coinfection on endothelial function in the HIV-1-infected cohort at baseline.
- 1.2.3 To assess whether non-hepatic biomarkers of endothelial dysfunction, inflammation, and thrombosis (sICAM-1, sE-selectin, Lp-PLA2, IL-6, and D-dimer) are better correlates of endothelial function than traditional hepatic-derived biomarkers (hsCRP and lipids) in HIV/HCV coinfecting in cross-sectional assessment at baseline.

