9.2 Endpoints

9.2.1 Primary Endpoints

9.2.1.1 Reactive hyperemia index (RHI) by PAT at baseline.

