9.2.2 Secondary Endpoints

9.2.2.1 Insulin resistance by HOMA-IR (fasting insulin ($\mu\text{U/mL}$) x fasting glucose (mg/dl)/405) at baseline and week 52.

9.2.2.2 Framingham risk score for 10-year CHD and 10-year CVD risk at baseline and week 52.

9.2.2.3 Cardiovascular biomarkers (fasting lipid panel, hsCRP, IL-6, D-dimer, sICAM-1, sE-selectin, Lp-PLA2) at baseline and week 52.

9.2.2.4 RHI by PAT at week 52

9.2.2.5 Change in RHI , biomarkers, HOMA-IR, and FRS from baseline to week 52.

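### Section 9.4.2 says it will settle whether non-hepatic markers correlate more strongly with RHI than hepatic ones in HIV/HCV, but plans no interval or test for that difference

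*Combined protocol and SAP*

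**What the plan says.** Section 1.2 lists as a primary objective (1.2.3) whether sICAM-1, sE-selectin, Lp-PLA2, IL-6 and D-dimer "are better correlates of endothelial function than traditional hepatic-derived biomarkers (hsCRP and lipids") in HIV/HCV subjects at baseline. Section 9.4.2 repeats this objective and plans:

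- a Pearson or Spearman correlation of each marker with RHI;
- matrices of the markers with each other and with RHI;
- confounder-adjusted regressions, one marker at a time;
- a combined model: "A final model will be constructed by including all significant biomarkers to predict RHI", summarised by its adjusted R-squared;
- the same in the other cohort: "Similar analysis will be carried out in HIV-monoinfected subjects only to derive the RHI prediction model";
- a comparison between cohorts: "The models for each cohort will be compared to each other for their predictive ability and differences in individual biomarker" significance.

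It then states: "This analysis will allow us to define whether non-hepatically-derived biomarkers have stronger correlation with RHI than hepatically-derived biomarkers".

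Three other places set the limits. The only primary endpoint (9.2.1) is "Reactive hyperemia index (RHI) by PAT at baseline". Section 9.3.1 says "The primary comparison is of baseline RHI between the HIV/HCV coinfecting and HIV monoinfected groups". The markers are secondary endpoints (9.2.2): "Cardiovascular biomarkers (fasting lipid panel, hsCRP, IL-6, D-dimer, sICAM-1, sE-selectin, Lp-PLA2) at baseline and week 52". Section 9.3.2 gives 80% power for a correlation above 0.31 between any one marker and RHI with 80 subjects, and above 0.42 with 40.

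**The concern.** 'Better' is a contrast between two classes of marker in the same subjects. None of the listed steps attaches uncertainty to that contrast, and there is no rule for when 'better' may be concluded. The final model mixes both classes and has one R-squared, so it does not separate them. The between-cohort step asks whether HCV status changes the marker model, and it does so partly by comparing which markers reach significance in groups of 80 and 40.

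Followed as written, the section could report a ranking that arose by chance, or a marker that looks specific to HCV because one cohort is twice the size of the other, as an answer to a primary objective.

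**Working it through.** **1. Does any step deliver the contrast?**

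| Planned step (9.4.2) | What it gives | Uncertainty on non-hepatic minus hepatic in HIV/HCV? |
|---|---|---|
| Marker-RHI correlations, matrices | Each r, and r between markers | No; differences can be computed, but no interval or test is planned |
| One-marker regressions | Each adjusted slope | No |
| Final model, adjusted R-squared | Mutually adjusted slopes of selected markers; one R-squared | No |
| HIV/HCV model against HIV model | A cohort difference | No; different question |

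The Benjamini-Hochberg reporting in 9.4.1 adjusts p-values and does not contrast classes.

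**2. The plan's own power figure.** One correlation against zero, two-sided 0.05: power = Phi(atanh(r) × sqrt(n − 3) − 1.96).
- n = 80, r = 0.31: 0.3205 × 8.775 − 1.96 = 0.853, power 80.3%.
- n = 40, r = 0.42: 0.4477 × 6.083 − 1.96 = 0.763, power 77.7% (78.7% with the small-sample bias term, 81.4% by noncentral t).

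Section 9.3.2 is right for what it covers, which is one marker against zero.

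**3. Comparing significance between cohorts.** Same true r in both cohorts; power from 200,000 simulated studies per r. The cohorts are independent, so P(only HIV/HCV) = p80 × (1 − p40) and P(only HIV) = p40 × (1 − p80).

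| True r | p80 | p40 | Only HIV/HCV | Only HIV |
|---|---|---|---|---|
| 0.20 | 0.433 | 0.236 | 0.433 × 0.764 = 33% | 0.236 × 0.567 = 13% |
| 0.31 | 0.809 | 0.504 | 0.809 × 0.496 = 40% | 0.504 × 0.191 = 10% |
| 0.42 | 0.976 | 0.789 | 0.976 × 0.211 = 21% | 0.789 × 0.024 = 2% |

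**4. Comparing significance within HIV/HCV.** Two markers with equal true r and an assumed inter-marker r of 0.3, n = 80: exactly one is significant in 40% of samples at r = 0.20 and 27% at r = 0.31.

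**5. What a contrast at n = 80 can show.** The documents give neither inter-marker correlations (rx) nor the number of lipid fractions, so both are assumed over a range, with no covariates.

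*Pairwise, 0.31 against 0.10.* The Meng-Rosenthal-Rubin test for two correlations that share RHI is z = [atanh(r1) − atanh(r2)] × sqrt{(n − 3)/[2(1 − rx)h]}, with m = (r1² + r2²)/2, f = min{1, (1 − rx)/[2(1 − m)]} and h = (1 − f·m)/(1 − m). For rx = 0.3: m = 0.053, f = 0.370, h = 1.035, z = 0.2202 × sqrt(77/1.449) = 1.605, power = Phi(1.605 − 1.96) = 36%.

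| rx | Power, formula | Power, simulated Williams test | 95% CI half-width for r1 − r2 | n for 80% power |
|---|---|---|---|---|
| 0 | 27% | 27% | 0.30 | 336 |
| 0.3 | 36% | 37% | 0.25 | 238 |
| 0.5 | 47% | 49% | 0.21 | 172 |

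*Class average.* Mean absolute r of the five non-hepatic markers minus that of the hepatic markers, percentile bootstrap, 2 to 5 hepatic markers, rx 0.15 to 0.5:
- all markers equal: non-hepatic falsely called better in at most 2.9%, wrong in either direction in at most 6.1%;
- all five at 0.31 and all hepatic at 0.10: power 59-83%, CI half-width 0.10-0.14;
- two of five at 0.31, the rest at 0.10 (3 to 5 hepatic markers): power about 12-21%;
- one of five at 0.42 (same settings): about 7-14%.

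**6. Cohort interaction in all 120.** SE = sqrt(1/77 + 1/37) = 0.200; 80% power needs a Fisher-z difference of 2.80 × 0.200 = 0.56, and tanh(0.56) = 0.51, so about r = 0.51 against 0.

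**The case against.** The best defence is that the raw material is already planned. The correlations and matrices, with n, are all that a Williams- or Steiger-type comparison of Pearson correlations needs. The final model gives mutually adjusted slopes for significant markers of both classes. This stands: a reader might infer that the plan has no estimate bearing on the objective, and that is not so. What it lacks is a planned interval or test for the difference.

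A second defence is proportion. The Rationale says the project is meant to produce preliminary data for further funding, and the objective is only to assess. That also stands, and it makes softer wording an acceptable minimum. It does not excuse a promise to 'define' the answer.

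A third is that chance gaps look worse for single pairs than for classes. Two markers with equal true r (0.20 or 0.31) differ by more than 0.20 in observed absolute r in 6-18% of studies at n = 80, for inter-marker r from 0.5 down to 0. A reader might take this as the error rate for the objective. It is not: averaged over classes (inter-marker r 0.3-0.5), a gap above 0.20 arises in under 1% of studies and one above 0.10 in about 5-18%. The 0.20 threshold also comes from no section of the plan.

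**Conclusion.** The point holds as a gap between the claim in 9.4.2 and the analysis planned for it. No interval, test or decision rule covers the non-hepatic minus hepatic difference within HIV/HCV. The one comparison that is stated can show an apparent cohort difference from sample size alone (40% against 10% at a common r of 0.31). It should be fixed.

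Two wider inferences are not supported. The primary endpoint and primary comparison concern baseline RHI and are untouched. The power in 9.3.2 is correct and limited to one marker; it is not a wrong figure, only one that does not extend to this contrast.

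Nor should the class-average power of 59-83% be read as what the study will have. It needs every non-hepatic marker at 0.31 and every hepatic one at 0.10. All contrast figures rest on normal data, assumed inter-marker correlations, an assumed number of hepatic markers, and no covariate adjustment. The omission itself is certain from the text.

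**What to change.** 1. In 9.4.2, within the 80 HIV/HCV subjects, report the difference in absolute correlation with RHI between non-hepatic and hepatic markers, with 95% intervals. Name the lipid fractions beforehand. Give both the class-average difference (bootstrap interval, usable with Pearson or Spearman) and the pairwise differences (Williams/Steiger-type or bootstrap interval, Benjamini-Hochberg across pairs), because the average dilutes a signal carried by one or two markers.
2. Conclude 'better' only if the interval excludes zero. Otherwise call the ranking descriptive, and soften 'define' accordingly.
3. If cohort differences are reported, use a marker-by-HCV-status interaction in the pooled 120 instead of comparing significance.
4. In 9.3.2, note that the one-marker power does not cover this contrast, and give its expected precision over a range of inter-marker correlations.

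The cost is SAP wording and an extra analysis of data already being collected. The drawback is a less favourable power statement and a greater chance of an inconclusive answer; the interaction in item 3 detects only large differences. If the team prefers no formal contrast, rewording the closing sentence of 9.4.2 as descriptive is the minimum.
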